8.1.1 SYSTEM OVERVIEW

The Biolinq MicroArray Intradermal Continuous Glucose Biowearable System consists of multiple components broadly categorized as follows:

- i. Biolinq Microarray Sensor
- ii. Biolinq wearable
- iii. Biolinq applicator

The Biolinq sensor consists of a sterile microarray sensor stack assembly that resides in the upper strata of the reticular dermis to measure interstitial glucose. The sensor is directly connected to a wearable that is adhered to the skin and is applied using the Applicator assembly. The Biolinq System measures and reports glucose information for up to five (5) days. The Biolinq System is designed to measure glucose levels for up to five (5) days. The wearable applied may also contain non-medical device designated off the shelf-components that capture actigraphy and environmental information to transfer to secondary display

8.2 OTHER STUDY DEVICE/MATERIALS

8.2.1 COMMERCIAL CGM

8.2.2 SELF-MONITORING BLOOD GLUCOSE (SMBG)

[REDACTED]

8.2.3 ACTIVITY TRACKER AND ELECTRONIC SUBJECT LOG

Subjects will be provided with an activity tracker device to wear throughout the study to capture subject activity levels.

[figure not shown]
[REDACTED]

[figure not shown]
[figure not shown]
8.2.4 LABORATORY ANALYZER

During In-Clinic Days, the FDA-cleared laboratory analyzer (LA) [YSI 2300 STAT PLUS Analyzer (Yellow Springs, Ohio)] will be used to measure venous sample glucose concentrations. Venous samples will be drawn according to a pre-specified protocol schedule and per the In-Clinic Guidelines located in Appendix 1 – In-Clinic Guidelines.

9 POTENTIAL RISKS AND BENEFITS**9.1 STUDY DEVICE RISKS**

[REDACTED]

**10 RATIONALE FOR THE STUDY DESIGN**

DCO-2025-0014

All subjects will wear a minimum of one Biolinq wearable each; a random subset of subjects will wear two wearables simultaneously for precision analysis. The study enrollment is designed to ensure a diverse population is evaluated when establishing a potentially new commercial product in the United States and other countries where the data may also be accepted to support marketing authorization.

11 STUDY OBJECTIVES

11.1 PURPOSE OF STUDY

The primary objective of the study is to evaluate the safety and effectiveness of the Biolinq MicroArray Intradermal Continuous Glucose Biowearable System, which is intended to be worn for up to five (5) days (up to 120 hours) in adults with diabetes mellitus (DM). Data collected from this study is intended to be used to support commercial marketing application(s) for the intended commercial patient population of non-insulin-users.

11.2 CO-PRIMARY PERFORMANCE ENDPOINTS

Biolinq System performance will be characterized with respect to laboratory reference venous measurements. The primary endpoint, matched paired (Sensor-YSI) measurements, will be collected during multiple in-clinic sessions on days 1, 3, and/or 5 of wear.

- For all available matched pair data points when the Biowearable displays BLUE (“in target” color indicator), the percentage of reference blood glucose values between 55-207 mg/dL must be calculated, and the lower one-sided 95% confidence bound [REDACTED]
- For all available matched pair points when the Biowearable displays YELLOW (“above target” color indicator), the percentage of reference blood glucose values between 154-460 mg/dL must be calculated, and the lower one-sided 95% confidence bound [REDACTED]

11.3 DEVICE SAFETY

Safety of the Biolinq System will be characterized by the:

1. Overall adverse device effect rate
2. Individual adverse device effect rates
3. Distribution of Draize assessments for erythema and edema for Biolinq Biowearable by Adverse Device Effects (ADEs) and Serious Adverse Device Effects (SADEs) experience by study participants.

11.4 DEVICE PRECISION

Randomization for 30% of subjects treated will receive a second Biolinq Biowearable to analyze device precision. Randomization scheme will ensure equally weighted assignments obtained from all participating clinical sites.

12 STUDY POPULATION

To attain sufficient hypoglycemia and hyperglycemia values in the study, the study will enroll subjects outside the intended commercial population of non-insulin-users. Enrollment efforts should attempt to include a 1:1 ratio of male to female subjects. Each site will be provided with a Site Enrollment Plan for diabetes type by the Sponsor to ensure target study population goals are met study wide.

■ [REDACTED]

■ [REDACTED]

12.1 DIVERSITY PLAN

In addition, the Site Enrollment Plan will include a Diversity Plan to attain the desired distribution of traditionally underrepresented populations. [REDACTED]

12.2 INCLUSION CRITERIA

Individuals may be included in the study if they satisfy all the following:

General

1. ≥ 22 years old.
2. Willing and able to provide written signed and dated informed consent.
3. Access to phone or computer with internet to complete subject log.

Diabetes History and Health

4. Diagnosis of type 1 diabetes (T1D)/ LADA or type 2 diabetes (T2D) and on intensive insulin therapy (IIT) with known dosing parameters for at least three (3) months prior to the Screening Visit with an A1c of 5.5%-10% or diagnosis of type 2 diabetes (T2D) and on non-intensive insulin therapy (NIIT) or T2D not using insulin with an A1c of 7.5% to 11%.
5. Weigh at least 110 lbs (50 kilograms).
6. Be otherwise in good health, as determined by a medical care professional.
7. Willing to refrain from Acetaminophen use for the duration of study enrollment.
8. If using an automated insulin delivery (AID) system, willing to disable automated features and go into open loop mode during the duration of in-clinic days.

Device and Glucose Assessments – Willing to:

9. Wear one (1) commercial CGM system ([REDACTED] on the abdomen per approved labeling and have up to 1 replacement.
10. Wear up to two (2) Biolinq Biowearables simultaneously following the application procedures on the volar forearm for up to 7 days.

11. Participate in two (2) In-Clinic sessions lasting up to 11.5 hours of blood draws (anticipated up to 13 hours on site per visit) each.
12. Perform up to five (5) fingersticks a day with the SMBG device provided during non-in-clinic days.
13. Avoid immersing study devices into water (e.g., no hot tub, SCUBA diving).
14. Wear an activity tracker or record activity levels on a daily log.

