5 SCHEMA

6 SCHEDULE OF ACTIVITIES (SOA)

7 INTRODUCTION

There are 27 million people in the US with Type 2 diabetes on non-insulin therapies and three million with Type 2 diabetes requiring basal insulin only.^{1,2,3} At a population level, glycemic control in people with diabetes has worsened over the past 10-15 years despite the introduction of six new drug therapeutic categories, as published in the New England Journal of Medicine.⁴ Recent studies have demonstrated CGM's effectiveness in people with Type 2 diabetes, including those not using insulin,^{5,6,7} and the American Diabetes Association recommends CGM use in persons with Type 2 diabetes. ADA recommends intermittent use of CGM to aid in evaluating periods of hyperglycemia to make medication dose adjustments.⁸ Despite these recommendations, less than 1% of the Type 2 non-insulin using population are estimated to be using conventional CGM. Commonly cited barriers to conventional CGM adoption for all diabetes populations include cost, discomfort/pain on insertion, skin/adhesive problems, size/form factor, disruptive alerts, and difficulty interpreting CGM data.^{9,10}

The absence of a device specifically designed to support disease management for people with Type 2 diabetes leaves these individuals with inadequate options to improve metabolic health. Currently, people with Type 2 diabetes are required to make the choice between using CGMs designed and optimized for people with Type 1 diabetes or continuing to rely on discrete blood glucose measurements produced by test strips. These blood glucose measurements can be painful and inconvenient to use and provide limited context on personal health trends and patterns, including the impact of food, medications, and activity on glycemic variability. Given the rising rates of Type 2 diabetes and prediabetes globally, as well as the increased risk for diabetes diagnoses following COVID-19 infection, there is a clear and growing need for more accessible, less invasive, and easier-to-use CGM devices designed specifically for people with Type 2 diabetes.

The primary objective of the study is to evaluate the safety and effectiveness of the Biolinq MicroArray Intradermal Continuous Glucose Biowearable System over a 5-day period in adults with diabetes mellitus. Data collected from this study is intended to be used to support commercial marketing application(s) for the intended commercial patient population of non-insulin-users.

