17.1.2 TREATED COHORT (ANALYSIS POPULATION)

All enrolled subjects who have undergone device application will be included in all analyses. All data that is collected during the study will be included in the analysis.

[figure not shown]

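### Does a 7-day wear ceiling in inclusion criterion 10 let wear beyond the 5-day claim distort the safety and precision results?

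*Combined protocol and SAP*

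**What the plan says.** - **Criterion 10**, in section 12.2 and again in the synopsis, is listed under the things a subject must be willing to do. It covers wearing up to two Biowearables "simultaneously following the application procedures on the volar forearm for up to 7 days".
- **The objective**, in section 11.1 and the synopsis, concerns a system "which is intended to be worn for up to five (5) days (up to 120 hours".
- **The introduction** (section 7) sets the evaluation "over a 5-day period in adults with diabetes mellitus".
- **The device description** (section 8.1.1) says the system "measures and reports glucose information for up to five (5) days".
- **The co-primary matched pairs** (section 11.2) "will be collected during multiple in-clinic sessions on days 1, 3, and/or 5 of wear".
- **The analysis population** (section 17.1.2) is every subject with a device applied, and "All data that is collected during the study will be included in the analysis".
- **The safety methods** (section 17.2) summarise adverse events by frequency and percentage, with the percentage of subjects affected. The Draize analysis is partly redacted.

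**The concern.** The 7-day and 5-day figures both stand in current text, and the 7-day figure appears twice. Criterion 10 speaks of simultaneous wear and mentions no replacement, whereas item 9 allows one for the commercial CGM, so consecutive devices are not an obvious explanation. If devices stay on past 120 hours and every observation is analysed, adverse device effects and Draize scores could reflect more skin exposure than the claim covers. Precision between paired devices could likewise draw on readings from sensors past their stated life. Safety over the intended wear is part of the primary objective, so a blurred window would matter for what the safety tables describe.

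**Working it through.** **Step 1. The plan's own figure.** 5 days × 24 = 120 hours, which matches section 11.1. Criterion 10 gives 7 × 24 = 168 hours.

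**Step 2. The most that could lie beyond the claim.** 168 − 120 = 48 hours. This is 48/120 = 40% more wear, or 48/168 = 28.6% of a full 7-day wear. With 206 treated subjects and 30% wearing a second device (0.30 × 206 = 61.8, about 62), there are about 268 devices. At most 268 × 48 = 12,864 device-hours could fall after 120 hours, against 268 × 120 = 32,160 within it. This assumes that every device stays on for 7 days and none is replaced.

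**Step 3. Whether 40% more hours means a 40% higher event rate.** Section 17.2 reports the percentage of subjects with an event. Assume a constant hazard, a 5-day percentage p and full 7-day wear. The 7-day percentage is then 1 − (1 − p)^(7/5). The documents give no value of p, so a range is shown:

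| Assumed 5-day rate | 7-day rate | Relative rise |
|---|---|---|
| 2% | 2.8% | 39% |
| 5% | 6.9% | 39% |
| 10% | 13.7% | 37% |
| 20% | 26.8% | 34% |

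The 40% is therefore a ceiling. It is approached only for rare events and only if every device is worn for the full 7 days. The percentage of subjects with at least one event cannot fall as wear lengthens, so the error runs against the device.

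**Step 4. Which results could be affected.**
- *Co-primaries:* the reference pairs are tied to wear days 1, 3 and/or 5, so they are not visibly affected.
- *Precision:* section 8.1.1 has the device reporting for up to 5 days, so the visible text does not show that readings exist after 120 hours. The synopsis redacts how precision is assessed, and section 11.4 gives only the 30% allocation. No effect can be shown.
- *Safety:* an effect is possible, because skin exposure does not depend on the sensor still reporting. The visible outcomes in sections 11.3 and 17.2 are descriptive, with no visible performance goal or test.

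**Step 5. Whether the texts truly conflict.** Section 8.1.1 limits measuring and reporting; only the objective puts a figure on intended wear. Criterion 10 is an upper limit on willingness, in the same form as item 11 (length of blood-draw sessions) and item 12 (daily fingersticks). The content that would give the removal day and any data window is redacted or not shown: the schedule of activities, duration of participation, study procedures, performance-metric definitions and device data download.

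**Step 6. What a 120-hour limit on safety data would do.** A device removed at 120 hours can leave a reaction that appears or worsens afterwards. The protocol captures these on purpose: adverse-event monitoring through study exit (synopsis), possible follow-up after removal (section 16.3) and skin-site evaluation after removal (section 22). A limit on time since application would move such events out of the main rate, although they arose from exposure within the claim.

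**The case for a change.** The best case for a change is that it is cheap and settles a choice in advance. Both figures are visible, sites need one meaning for the wear period (exclusions 9, 10 and 11f and a study-exit rule in the synopsis rely on it), and the visible analysis text does not separate events by wear time. If the 7 days is only scheduling tolerance, some devices may still stay on past 120 hours, and it is better to decide beforehand how those events are shown.

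Part of this stands. The wear statements in criterion 10 and the objective differ and must be reconciled, and this review does not say which duration is right. The rest does not carry to a change in the analysis. Whether any device is worn past 120 hours depends on text that is not shown, and that text may already contain a rule. Keeping every event is the cautious choice for safety. Removal dates are recorded for each device under section 24.3, so an analyst can flag events arising from wear beyond 120 hours while keeping them in the main tables.

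**Conclusion.** The mismatch is real, but it is one of wording: a willingness limit of 168 hours beside an intended wear of 120 hours. It does not show that subjects are scheduled to wear the device for 7 days, and it changes no visible co-primary result. The precision consequence is unsupported. For safety, the worst case is a relative rise of about 34% to 39% in the percentage of subjects with an event, for assumed 5-day rates between 20% and 2%. It rests on full 7-day wear for everyone, a constant hazard and no replacement, none of which the documents state, and it would make the device look worse. The all-data rule in section 17.1.2 should stand, because a 120-hour limit on safety data risks losing delayed reactions to wear within the claim. Apart from reconciling the two wear statements, which hidden sections may already do, no change to the design or analysis follows.

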12.3 EXCLUSION CRITERIA

Individuals with any of the following will be excluded:

General

1. Current participation in another investigational study protocol. (If a subject has recently completed participation in another drug study, the subject must have completed that study at least 30 days prior to being enrolled in this study.) *Note:* Subjects will not be excluded if enrolled in another observational trial, wherein the subject is in the follow-up phase and no tests/procedures impacting the subject's health are required. Subjects will be excluded if they have been previously enrolled in this study.
2. Work for, are family members with, or live with someone that works for the sponsor or competitor diabetes-related company (includes social media influencers or bloggers).
3. In the investigator's opinion, any reason that may lead to subject non-compliance with study requirements or confound study data.

Health

4. Currently taking Hydroxyurea.
5. Known allergy to medical grade adhesives, acrylic, latex, or isopropyl alcohol.
6. Have dermatological conditions that preclude wearing BiolinQ Biowearables (e.g., extensive psoriasis, recent burns, severe sunburn, extensive eczema, extensive scarring, dermatitis herpetiformis, skin lesions, erythema, infection, or other conditions at the discretion of the investigator).
7. For subjects of child-bearing potential, pregnant or not practicing an acceptable form of birth control during the study.
8. Hematocrit measurement via point-of-care (POC) or laboratory testing that is less than the applicable below-mentioned value:
 - a. Male: 36.0%
 - b. Female: 33.0%
9. Have donated blood, had significant blood loss, or participated in a study with significant blood sampling (340 cc or more) within 56 days prior to study enrollment or plan to participate in such activities during study wear.
10. Required or scheduled to have diathermy, X-ray, MRI, or CT during study wear.
11. In the investigator's opinion, the subject has a history of concomitant medical condition that could interfere with the study participation or present a risk to the safety and welfare of the subject or study staff. Such historical conditions include but are not limited to:
 - a. Syncope in past 6 months
 - b. Severe hypoglycemia (loss of consciousness, seizure, or emergency medical technician assistance within the past 6 months)
 - c. Diabetic ketoacidosis (DKA) requiring hospital admission in the past 6 months
 - d. Coagulopathy
 - e. Chronic infectious disease (e.g., HIV/AIDS, Hepatitis B or C)
 - f. End stage renal disease and currently managed by dialysis or anticipating initiating dialysis during the study wear period
 - g. History of congestive heart failure

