4 PROTOCOL SYNOPSIS

Table 2 Protocol Synopsis

Title:	Safety and Effectiveness Study of the BioliniQ MicroArray Intradermal Continuous Glucose Biowearable System
Study Sponsor:	BioliniQ, Incorporated
Investigational Device:	BioliniQ System: BioliniQ MicroArray Intradermal Continuous Glucose Biowearable System.
Reference Device:	FDA-cleared Laboratory Analyzer (LA) [YSI STAT PLUS 2300 Glucose and L-Lactate Analyzer (Yellow Springs, Ohio)]
Comparator Devices:	
The following commercially available comparator devices will be used to collect glucose data for reference analysis:
 
• Self-monitoring blood glucose (SMBG) meter: [REDACTED]• Continuous Glucose Monitor (CGM): [REDACTED] [REDACTED]
Design:	Clinical safety and effectiveness study – open label, prospective, multi-center, single arm
Objectives:	The primary objective of the study is to evaluate the safety and effectiveness of the BioliniQ MicroArray Intradermal Continuous Glucose Biowearable System, which is intended to be worn for up to five (5) days (up to 120 hours) in adults with diabetes mellitus (DM). Data collected from this study is intended to be used to support commercial marketing application(s) for the intended commercial patient population of non-insulin-users.
Study Population	To attain sufficient hypoglycemic and hyperglycemic values in the study in conjunction and ensure that underrepresented populations are included in the evaluation, the study will enroll subjects outside the device's intended population and include persons requiring insulin for management of their disease. [REDACTED]
Number of Subjects:	Enroll up to 247 subjects to ensure at least 206 subjects are treated allowing for up to 18.2% screen failures.

Number of Centers:	A minimum of five (5) and up to eight (8) centers in the United States will participate in the study.
Estimated Duration:	
Randomization	The study will utilize three (3) independent randomization assignments with 1:1 ratio for the location of the biowearable (left vs. right volar forearm), 7:3 ratio for the number of biowearables (one vs. two), and the 1:1 ratio for the primary biowearable determination (proximal vs. distal) for subjects who were randomized to wear two biowearables.

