----------------------------	--

Methodology:	This is an open label, single arm, multi-center study conducted in 5-8 investigational sites in the United States. Enroll up to 247 subjects to yield at least 206 treated subjects assuming up to 18.2 % screen failures.
Consent and Screening:	Subjects are considered enrolled after signing and dating an Institutional Review Board (IRB) approved informed consent form (ICF). activities must be completed within 30 days prior to the Bioliniq application and include eligibility criteria, vitals, demographics, medical history review, Fitzpatrick Skin assessment, pregnancy testing (as applicable), A1c and hematocrit tests. Subjects who meet the study eligibility criteria will be scheduled for Bioliniq Biowearable application. Screen failures must exit the study and reasons for exit are documented. Subjects who do not complete screening activities within 30 days are still eligible to participate in the study but must be reconsented and re-screened.
Subjects who passed the screening activities will be randomized	[REDACTED]

[figure not shown]
The YSI STAT PLUS 2300 Glucose and L-Lactate Analyzer will be used to measure glucose values (reference data) for all blood draws during in-clinic sessions. Four active venous blood draws will be done every hour (one blood draw every 15 ± 7 minutes). A matching SMBG fingerstick on the same arm as the BioliniQ Biowearable will be taken simultaneously with the draw for three (3) out of every four (4) blood draws for comparative purposes.

[figure not shown]
Using glucose measurements taken under close direction and observation of the investigator staff, insulin dosing (for subjects on insulin) and meal composition/timing may be manipulated during the in-clinic session to obtain sufficient data variation between 40-400 mg/dL and attain sample sizes required for performance evaluation to support device commercial application.

[figure not shown]

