14.3 ENROLLMENT

Subjects who sign the IRB approved ICF will be considered “Enrolled” in this study.

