17.1.1 ENROLLED COHORT

The Enrolled Cohort includes all subjects who sign the study IRB approved informed consent. Analyses pertaining to screening eligibility, safety, and protocol compliance prior to the Bioliniq application, and study exit will be performed using the Enrolled Cohort.

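### Does the bar on previously enrolled subjects shut out those who re-consent after the 30-day screening window lapses?

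*Combined protocol and SAP*

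**What the plan says.** The Exclusion Criteria (section 12.3, item 1, and the same item in the synopsis) end with an unqualified sentence: "Subjects will be excluded if they have been previously enrolled in this study".

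Enrolment is tied to consent in three places: the synopsis under Consent and Screening, section 14.3 ("Subjects who sign the IRB approved ICF will be considered" enrolled), and section 17.1.1 ("The Enrolled Cohort includes all subjects who sign the study IRB approved informed consent").

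The synopsis limits screening to the 30 days before device application and then deals with overruns: "Subjects who do not complete screening activities within 30 days are still eligible to participate in the study but must be reconsented and re-screened". Just before this, it says that screen failures must leave the study with the reason recorded.

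The enrolment target in the synopsis is: "Enroll up to 247 subjects to ensure at least 206 subjects are treated allowing for up to 18.2% screen failures".

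**The concern.** Put the definition and the exclusion together and a lapsed subject appears to be barred. The first signature made that person enrolled. At re-screening the person has therefore been enrolled before, and criterion 1 has no exception. The synopsis calls the same person eligible. A site following one sentence would break the other.

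Three things would be at stake:

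- Five to eight sites might resolve the conflict differently, some turning people away and others treating them and logging an eligibility deviation.
- If each signature counted as an enrolment, a re-consented person would use two of the 247 places and appear twice in the Enrolled Cohort. That would distort the screen-failure rate.
- The cap has little slack, so lost places could reduce the number treated.

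**Working it through.** **The rules side by side**

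| Rule | Where | Applied to a lapsed subject |
|---|---|---|
| Enrolled on signing consent | Synopsis; 14.3; 17.1.1 | Enrolled at first signature |
| Previously enrolled means excluded | Synopsis; 12.3 item 1 | Excluded, if the first signature counts as previous enrolment |
| Window overrun means still eligible after re-consent and re-screening | Synopsis, Consent and Screening | Eligible |
| Screen failure means exit | Synopsis, Consent and Screening | Does not apply; overruns are handled separately |

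The conflict depends on the word *previously*. The Study Exit text in the synopsis lists screen failure, failure of all devices, completion, loss to follow-up, withdrawal of consent and withdrawal by the investigator. A lapsed window is not on the list. Someone who has not exited is still enrolled, and the words *still eligible* fit that. The criterion also sits in an item about participation in other studies and repeat participation in this one, which suggests its target is a person coming back for a second time.

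**What is counted.** The synopsis caps subjects at 247. Sections 14.3 and 17.1.1 speak of subjects who sign. Section 18.3 refers to a unique identification code for each subject. One person who signs twice is one subject in each of these, so the double count does not follow from the text.

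**Size.** The plan states no figure for lapses, so there is none to reproduce. The only related figures are the enrolment numbers in the synopsis:

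- Places for subjects who are not treated: 247 − 206 = 41, and 41/247 = 16.6%.
- Treated at the stated 18.2% failure rate: 247 × (1 − 0.182) = 202.0, which is 4 below 206. This is a separate matter of enrolment arithmetic and exists with or without any lapse.
- Assumed lapse rate of 2% to 5% (not in the documents): 247 × 0.02 = 4.9 and 247 × 0.05 = 12.4, so about 5 to 12 people.
- Places lost to a second signature when subjects are counted: 0.
- Places lost if signatures were counted, against the text: 5/41 = 12% to 12/41 = 29% of the 41.

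**Effect on the analysis.** Section 17.1.2 includes every enrolled subject who has undergone device application. A re-consented subject who passes re-screening and wears the device contributes the same matched pairs and the same safety data, whichever sentence is thought to govern.

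**The case for a change.** The strongest case for a change is that neither rule refers to the other. The exclusion stands in both eligibility lists, while the exception is visible only in the synopsis narrative. Asking for consent again, the very act that defines enrolment, makes the lapsed subject look like a new entrant. Section 21.1.1 treats any unmet requirement as a deviation, so a strict monitor could query these subjects. The text also does not say which signature sets the enrolment date for the 30-day gap after another drug study (criterion 1) or the 56-day blood-loss window (criterion 9).

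The literal mismatch stands, and a cross-reference would have been tidier. The rest is weaker. A rule that names the situation qualifies a general bar, and a site with a lapsed subject would look to the screening rule first. Re-screening means checking the criteria again at the later date, which settles the look-back windows in practice. The body of section 14.4 (Screening) is not visible in the public text, so it cannot be assumed to lack a clarification.

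The obvious rewording also has a cost. Barring only those who have already had a Biowearable applied would readmit screen failures and people who withdrew before application, whom the present wording keeps out. That widens eligibility to cure a drafting slip.

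**Conclusion.** The wording conflict is real but clerical, and the plan needs no change. The screening rule in the synopsis gives sites a clear answer for this case. Subjects, not signatures, are counted toward the 247 and in the Enrolled Cohort. The analysis population is fixed by device application, so no endpoint, estimate or confidence bound moves. At an assumed 2% to 5% lapse rate, some 5 to 12 people would be affected, with no places lost; the worst consequence is a monitoring query.

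This rests on two assumptions: that sites follow the specific rule over the general one, and that a re-consented subject keeps a single identification code, as section 18.3 implies. The gap between 202 and 206 treated at 18.2% screen failures is a different question and gives this one no weight.

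### Exclusion 9 (blood donation, blood loss, heavy study sampling) does not cover the interval between consent and Biowearable application

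*Combined protocol and SAP*

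**What the plan says.** Exclusion 9 in section 12.3, repeated in the synopsis, names three events: donating blood, significant blood loss, and taking part in a study with significant blood sampling, which the item puts at 340 cc or more. It applies if the event fell "within 56 days prior to study enrollment or plan to participate in such activities during study wear".

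Three other provisions fix what those two periods mean in calendar time:

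- Section 14.3: "Subjects who sign the IRB approved ICF will be considered" enrolled. The Consent and Screening text of the synopsis and the Enrolled Cohort definition in 17.1.1 agree that enrolment is the signing of consent.
- Synopsis, Consent and Screening: "activities must be completed within 30 days prior to the Bioliniq application". The same list includes "pregnancy testing (as applicable), A1c and hematocrit tests".
- Synopsis, same place: "Subjects who do not complete screening activities within 30 days are still eligible to participate in the study but must be reconsented and re-screened".

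Section 12.2, item 11, states what the subject then undergoes: "Participate in two (2) In-Clinic sessions lasting up to 11.5 hours of blood draws". The Methodology text of the synopsis sets four venous draws per hour.

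**The concern.** The item looks back from consent and forward over wear. If application follows consent by some weeks, those weeks belong to neither period. They are also the weeks nearest to the serial venous sampling, so the losses that the item misses are the most recent ones.

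The hematocrit limits in exclusion 8 do not clearly fill the gap. In the readable text hematocrit appears only as a screening activity, so the value on file may come from before the loss.

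The issue is the safety of individual subjects. The co-primary endpoints, the sample size and the analysis cohorts do not depend on it.

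**Working it through.** The plan gives no figure to reproduce here. The check compares time windows and counts draws.

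**Inputs**

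- Look-back: 56 days before enrolment (12.3, item 9).
- Forward limb: plans during study wear (12.3, item 9).
- Enrolment: signing consent (14.3; synopsis; 17.1.1).
- Consent-to-application interval, *g*: 0 to about 30 days (synopsis). The upper end takes the re-consent rule as limiting the time since consent. No typical interval is readable.
- Sessions: 2, with up to 11.5 hours of draws each (12.2, item 11).
- Draw rate: 4 per hour (synopsis, Methodology).
- Volume per draw: not in the readable text; assumed 1 to 4 mL.

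**Step 1: the uncovered interval.** Let consent be day 0 and application day *g*. Item 9 covers day -56 to day 0, and day *g* to the end of wear. Day 0 to day *g* is uncovered, so the gap is *g* days, up to about 30.

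**Step 2: share of the 56 days before application that the item covers**, (56 - *g*)/56:

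| *g* (days) | Covered days | Share |
|---|---|---|
| 0 | 56 | 100% |
| 7 | 49 | 87.5% |
| 14 | 42 | 75% |
| 30 | 26 | 46% |

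**Step 3: the resulting ordering.** With *g* = 30, a donation 56 + 30 = 86 days before application falls at the edge of the look-back and can exclude a subject. A donation on the day before application does not meet the item.

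**Step 4: sampling that follows.** 4 x 11.5 = 46 draws per session at most; 46 x 2 = 92 over two sessions.

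**Step 5: volume, under the assumption only.** 92 x 1 mL = 92 mL and 92 x 4 mL = 368 mL. The protocol's own 340 cc mark is reached at 340/92 = 3.7 mL per draw, near the top of the assumed range.

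**Step 6: after the change.** If the item runs from 56 days before enrolment to the end of wear without a break, the uncovered interval is 0 days for every *g*.

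**The case against.** The strongest reply is that other provisions already reach most of the events in the gap.

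- **Significant blood loss.** The synopsis has every subject monitored for adverse events from consent to study exit. Inclusion 6 requires otherwise good health. Section 22 ends participation for acute illness and allows withdrawal in the subject's best interest.
- **Heavy sampling elsewhere.** Exclusion 1 separately bars current participation in another investigational study.
- **Anything else.** Exclusions 3 and 11 leave room for the investigator's opinion.

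This stands in part. It leaves mainly a voluntary donation after consent, plus any loss that monitoring or judgement does not pick up. None of these provisions directs staff to ask about donation or blood loss after consent.

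A second reply is that the Schedule of Activities, sections 14.4 and 14.5, most of section 15 and section 26.1.4 are largely unreadable. A repeat hematocrit, an instruction not to donate or a blood-volume limit may be there. This also stands, and it limits what can be said about harm. It does not repair the wording: re-asking item 9 on the application day would still look back only from consent.

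A third reply is that 30 days and 92 draws are ceilings. That is correct; both are used here as upper limits.

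A reader might go further and infer that a subject with a fresh loss would pass the whole eligibility list and be sampled with a hematocrit below the exclusion 8 limit, unnoticed. The documents do not support that. The provisions above could each stop such a subject, exclusion 8 states no test date, and a repeat test cannot be ruled out.

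**Conclusion.** The gap holds on the wording of item 9 and the definition of enrolment; no redacted figure is needed to see it. It lasts from 0 to about 30 days, and at its longest leaves 30 of the 56 days before application uncovered.

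The size of the safety effect is unknown. Draw volume, the usual consent-to-application interval and any application-day checks are not readable, and probably few subjects are affected. It would also go too far to say that the 56 days are tied to the wrong date: the documents do not state the purpose of that period, and no two sections contradict each other. The supported point is that the item leaves a break between its two periods.

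This is a cheap improvement of minor severity, with no effect on endpoints, sample size or analysis.

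**What to change.** In section 12.3, item 9, and in the synopsis, keep the sponsor's 56-day look-back from enrolment and the 340 cc mark. Replace the second limb with wording such as: *or at any time from enrollment through the end of study wear, whether it has occurred or is planned*. Have the site confirm the item with the subject on the application day.

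This is preferable to moving the look-back to the application date, which would loosen the rule for some. A subject who donated 40 days before consent and has the device applied 20 days after it is excluded now, but would become eligible at 40 + 20 = 60 days. Extending the item forward closes the gap and admits nobody who is now excluded.

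The cost is one clause in two places and one question at the application visit. A very few screened subjects may be deferred. No procedure is added.
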